#### **Stopping Criteria**

Interim analysis will be performed after 50% enrolment. If either arm is found to be superior, the trial will be discontinued. If any adverse events are identified in either arm, a safety review will be performed. Should a significant safety concern be identified, the trial will be discontinued.

### Pharmacokinetics and Pharmacodynamics-Bupivicaine

Pharmacodynamics and Pharmacokinetics

Onset of action: Anesthesia (route and dose dependent):

Epidural: Up to 17 minutes to spread to T6 dermatome (Scott 1980).

Infiltration: Fast (Barash 2009); Dental injection: 2 to 10 minutes.

Spinal: Within 1 minute; maximum dermatome level achieved within 15 minutes in most cases.

Duration (route and dose dependent):

Infiltration: 2 to 8 hours (Barash 2009); Dental injection: Up to 7 hours.

Distribution:  $V_d$ : Infants:  $3.9 \pm 2$  L/kg; Children:  $2.7 \pm 0.2$  L/kg.

Protein binding: 84% to 95%.

Metabolism: Hepatic; forms metabolite (pipecoloxylidine [PPX]).

Half-life elimination (age dependent): Implant: 19 hours; Injection: Neonates: 8.1 hours; Adults: 2.7 hours; Subacromial injection: 16.4 to 26.1 hours.

Time to peak, plasma: Caudal, epidural, or peripheral nerve block: 30 to 45 minutes; Implant: Median: 3 hours (range: 1.5 to 24 hours); Subacromial injection: Median: ~6 to 8 hours (range: 1 to ~27 hours).

Excretion: Urine (~6% unchanged).

Clearance: Infants:  $7.1 \pm 3.2$  mL/kg/minute; Children:  $10 \pm 0.7$  mL/kg/minute.

## $Pharmacokinetics\ and\ Pharmacodynamics-Dexamethas on e^{36}$

Onset of action: IV: Rapid.

Immune thrombocytopenia: Oral: Initial response: 2 to 14 days; Peak response: 4 to 28 days

(Neunert 2011).

Duration: IV: Short.

Absorption: Oral: 61% to 86% (Czock 2005).

Metabolism: Hepatic. Half-life elimination:

Adults: Oral:  $4 \pm 0.9$  hours (Czock 2005); IV: ~1 to 5 hours (Hochhaus 2001; Miyabo 1981;

Rohdewald 1987; Tóth 1999).

Time to peak, serum: Oral: 1 to 2 hours (Czock 2005); IM: ~30 to 120 minutes (Egerman 1997;

Hochhaus 2001); IV: 5 to 10 minutes (free dexamethasone) (Miyabo 1981; Rohdewald 1987).

Excretion: Urine (~10%) (Duggan 1975; Miyabo 1981).

#### Selection and withdrawal of subjects

We intend to enroll a sample size of 120 patients based on an alpha set at 0.05, power set at 0.08, and the effect size set at 0.8.

Inclusion criteria are: age > 18, ASA class I-III patients scheduled for elective or urgent inpatient laparoscopic/laparoscopic assisted colorectal surgery.

Exclusion criteria are: emergency surgery, open surgery, contraindications to laparoscopic surgery (ie. adhesions, inability to tolerate pneumoperitoneum), ASA class  $\geq 4$ , age < 18, pregnant or breastfeeding women, significant cardiorespiratory/hepatic/renal disease, allergy to any study drugs, inability to consent, inability to respond to pain assessments, inability to use the patient-controlled analgesia device (PCA), preoperative chronic opioid use.

Potential participants will be identified by their attending surgeon during their initial clinic surgical consultation. This typically occurs several weeks in advance of their scheduled surgical procedure. Information detailing the study, as well as contact information of the research team will be made available to patients at this time should they have any questions. After having had a chance to review the study information provided to them by their surgeon, prospective patients will be assessed by study staff (attending surgeon or designate such as a general surgery resident) and asked to sign a consent if they agree to participate and meet the inclusion criteria. The consent will be taken on the day of surgery.

Participants who are unable to personally provide informed consent will be excluded from the study. No third party will be allowed to consent on the participants behalf. Capacity will be assessed by the study staff or designate obtaining consent. All patients participating must be assessed to determine that they fully understand the protocol, risks, and benefits of participating in the study.

Subjects will be free to withdraw voluntarily from the study at any point. The process for withdrawal can be initiated by the participant at any time by informing any of the study staff of the decision to withdraw. No explanation for withdrawal will be sought. If this occurs prior to randomization, no patient information will be collected for study purposes, and the patient will still be eligible to undergo surgery as planned without compromise to care. If withdrawal occurs during data collection, data collected on the subject will be destroyed, and they will continue receiving post-operative care as per standards. Either of the attending anesthesiologist or attending surgeon caring for the patient on the day of surgery has the ultimate discretion as to whether a patient is included or excluded from the study. If the attending surgeon or anesthesiologist deems the patient unfit to participate in the study, this will be communicated to the study coordinator, and the patient will be withdrawn. All adverse events and protocol deviations will be reported to the study coordinator, study investigators, and appropriate Research Ethics Board. Subjects who are withdrawn from the study due to the occurrence of an adverse event will be followed up by one of the study's physician investigators while in hospital. If the adverse event is believed to have been related to the study drug, a detailed note will be made in the patient's medical record and passed on to future care providers. Subjects withdrawn from the study due to an adverse event will not be replaced. Any adverse events will result in unblinding by notification of the principle investigator.

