A computer-generated random number table will be used to randomize patients to receive either bupivacaine alone (n=60) or bupivacaine plus dexamethasone (n=60). Allocation will be performed in a 1:1 ratio. Group allocation will be concealed via a centralized third-party research assistant. Group allocation will be blinded to study participants, study investigators, post-anesthetic care unit (PACU) nursing staff, and surgical ward nursing staff. The attending surgeon and attending anesthesiologist on the day of surgery will not be blinded to the intervention, however, they will be asked to conceal the anesthetic modality from the PACU staff and ward nurses. The intervention will be charted in the Operating Room record, but not on the anesthetic record. PACU nurses commonly review the anesthetic record, whereby they would discover the intervention.

A blinded, centralized, third-party research assistant or study investigators will carry out data collection. Postoperative opioid consumption will be quantified through chart review as well as assessment of patient-controlled analgesia (PCA) usage at 24 and 48 hours following the operation. Recording the doses of opioids administered in the medication administration record (MAR) is standard practice by PACU nursing staff at the study institution. PCA pumps automatically document cumulative opioids administered and can easily be checked at the bedside, as well as being recorded in the MAR. Length of stay in hospital is readily available from the chart.

Followup for primary and secondary outcomes will be limited to 48 hours postoperatively, and assessment of infiltration sites for complications will be performed at 6 weeks postoperatively.

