#### **Statistics**

Primary Outcome:

Total opioid consumption at 24 and 48 hours will be gathered from the PCA record and Medication Administration Record (MAR). Intention to treat analysis will be performed. Parametric data will be analyzed with the students t-test for statistical significance.

Secondary Outcome: Opioid consumption in the PACU will be reported in hydromorphone equivalents and compared with chi square test. Length of stay in PACU and length of stay in hospital will be reported as a mean +/- standard deviation (SD), along with confidence intervals and compared with chi square test.

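### The stated alpha, power and effect size do not give 120 patients, even after the evident misprint in the power is corrected

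*Protocol*

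**What the plan says.** The sample-size justification is a single sentence in Selection and withdrawal of subjects: "sample size of 120 patients based on an alpha set at 0.05, power set at 0.08, and the effect size set at 0.8". Trial Design divides the total equally by randomising patients "to receive either bupivacaine alone (n=60) or bupivacaine plus dexamethasone (n=60". The primary outcome is continuous: total opioid consumption over 48 hours, in hydromorphone equivalents. For its analysis, the Statistics section says: "Parametric data will be analyzed with the students t-test for statistical significance".

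The Protocol does not say whether alpha is one- or two-sided. It gives no unit, SD or source for the effect size, no dropout rate, and no adjustment of the sample size for the interim analysis.

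**The concern.** The sentence presents 120 as the result of three inputs, so a reader should be able to recover 120 from them. Two things stand in the way. "power set at 0.08" cannot be a design target. In addition, an effect of 0.8 SD is large, and a two-arm t-test needs far fewer than 60 per arm to detect it.

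The consequence depends on which input is wrong, and the document does not show which. If 0.8 SD is the real target, the trial enrols more than twice the number needed, including 34 additional patients (60 − 26) in the dexamethasone arm, who receive the drug by a route that Background Information describes as off-label. If the real target is nearer 0.5 SD, the printed effect size is wrong and power is a little under 80%. An ethics board or funder cannot tell these two cases apart from the text.

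**Working it through.** **Inputs.** Total 120, alpha 0.05, power 0.08 and effect size 0.8 come from Selection and withdrawal of subjects. The split of 60 and 60 at 1:1 comes from Trial Design. The t-test comes from Statistics. Two assumptions are needed: the effect size is a standardised mean difference d, and alpha is two-sided (one-sided is also tried).

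**Formulas.** Normal approximation: n per arm = 2(z_α + z_β)² / d², with z_α taken at alpha/2 for a two-sided test. Exact t-test: the smallest n for which a noncentral t with 2n − 2 degrees of freedom and noncentrality d√(n/2) reaches the required power.

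**Attempt to reproduce 120 with d = 0.8**

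- Two-sided, power 0.80: 2(1.960 + 0.842)² / 0.64 = 24.5, so 25 per arm. The exact t-test gives 25.5, so 26 per arm and 52 in total.
- Two-sided, 0.08 read as type II error (power 0.92): 2(1.960 + 1.405)² / 0.64 = 35.4, so 36 per arm. The exact t-test gives 36.4, so 37 per arm.

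| Reading | Per arm (t-test) | Total |
|---|---|---|
| Power 0.08 as printed, two-sided | 3 (2 per arm gives 0.079) | 6 |
| Power 0.80, two-sided | 26 | 52 |
| Power 0.80, one-sided | 21 | 42 |
| Power 0.92, two-sided | 37 | 74 |
| Power 0.92, one-sided | 30 | 60 |

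None comes near 120. The ratio for the most natural reading is 120 / 52 = 2.3.

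**Could an unstated allowance close the gap?**

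- Dropout: 1 − 52/120 = 57% loss would be needed from 52, and 1 − 74/120 = 38% from 74. A 20% loss gives only 65 or 93.
- Stricter alpha for an interim look (Pocock-type 0.0294): 30 per arm at power 0.80, 42 at power 0.92.
- Bonferroni alpha 0.025: 31 or 43 per arm.
- Rank test at its worst-case efficiency of 0.864: 26 / 0.864 = 30.1, so 31 per arm; 37 / 0.864 = 42.8, so 43 per arm.

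**What 60 per arm delivers (two-sided 0.05, t-test)**

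- Power at d = 0.8: 0.991. Normal check: 0.8 × √30 − 1.960 = 2.42, which gives 0.992.
- Power at d = 0.5: 0.775.
- Detectable d: 0.516 at 80% power, 0.597 at 90% power.
- If power really were 0.08, 60 per arm would correspond to d = 0.093.

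**Combinations that give about 120.** These are d = 0.52 at 80% power (60 per arm), d = 0.6 at 90% (60 per arm), and d = 0.8 at 99% (59 per arm). The Protocol states none of them. With d = 0.5 at 80% power, two-sided and without dropout, the answer is 64 per arm, 128 in total.

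**The case against.** The strongest reply is that "the effect size set at 0.8" carries no unit, so a standardised difference is only one interpretation. A raw difference of 0.8 mg would need 60 per arm at 80% power if the SD were 0.8 / 0.516 = 1.55 mg. A ratio of 0.8, meaning a 20% reduction, would do so if the coefficient of variation were 0.20 / 0.516 = 0.39. A one-sided test with d = 0.5 needs 51 per arm, 102 in total, and a 15% loss brings that to 102 / 0.85 = 120. These routes cannot be ruled out. However, each requires an SD, a coefficient of variation, a different effect or a dropout rate that the Protocol does not state, so none derives 120 from what is written. They strengthen the case for stating the unit and the SD.

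It is also fair to say that the error is in the safe direction for power. On the main reading the trial is oversized, not underpowered, and it keeps 78% power at d = 0.5. Some margin above 52 is sensible, because the Protocol destroys data on withdrawal, excludes patients given rescue dexamethasone, and does not replace adverse-event withdrawals. A margin of 57% is not credible on those grounds, and none is claimed.

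Finally, what a null result excludes will be read from its confidence interval, not from the planning effect. The case therefore rests on the justification of the trial's size, not on how its result would be interpreted.

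**Conclusion.** The sample-size statement is wrong as written, and it stays wrong after the obvious correction of 0.08 to 0.80. Read as a standardised difference with a two-sided t-test, the inputs give 52 patients against 120 planned. The power that 120 provides for 0.8 SD is 99%, and the difference detectable with 80% power is 0.52 SD.

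These figures assume 60 analysable patients per arm, a single test at 0.05, and data suited to a t-test. They make no allowance for dropout or for alpha spent at the interim analysis. The printed power is certainly an error. Beyond that, the document does not show whether the effect size is wrong, an allowance was left out, or 120 was chosen on other grounds. Because this sentence is the only justification for the size of the trial, it must be corrected.

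**What to change.** Replace the sentence in Selection and withdrawal of subjects with one that can be reproduced. For the planned 120, it could read: with 60 analysed patients per arm, a two-sided t-test at the 0.05 level has 80% power to detect a standardised difference of 0.52 in 48-hour opioid consumption, corresponding to a difference of X mg hydromorphone equivalents with an assumed SD of Y mg.

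The sponsor must supply X, Y and their source, and say why a difference of that size is worth detecting. Otherwise 0.52 is merely solved backwards from a fixed number. Any allowance for dropout or for the interim look should be stated in the same place, with the figure recalculated to include it.

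If 0.8 SD is the intended target, the Protocol should say that 120 gives 99% power and explain why that is wanted, or reduce the number to 52 plus a stated dropout allowance. A reduction would be a design change, not a rewording, and is not needed to resolve this point.

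Restating the figure for 120 costs one sentence and no additional patients.

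### Staff are directed not to ask why a participant withdraws, although two adverse-event rules turn on the reason, so a withdrawal driven by an unrecorded harm may be missed

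*Protocol*

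**What the plan says.** All the rules on leaving the trial stand in one part of the protocol, Selection and withdrawal of subjects.

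- Voluntary route: "The process for withdrawal can be initiated by the participant at any time by informing any of the study staff of the decision to withdraw". The next sentence is "No explanation for withdrawal will be sought".
- Clinician route: "If the attending surgeon or anesthesiologist deems the patient unfit to participate in the study, this will be communicated to the study coordinator", after which the patient is withdrawn.
- Consequences linked to an adverse event: "Subjects who are withdrawn from the study due to the occurrence of an adverse event will be followed up" by a physician investigator during the hospital stay, and "Subjects withdrawn from the study due to an adverse event will not be replaced".
- General reporting: "All adverse events and protocol deviations will be reported to the study coordinator, study investigators, and appropriate Research Ethics Board".
- Data: what has been collected on a participant who withdraws during data collection is to be destroyed.

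The section Assessment of safety adds daily and six-week examination of the injection sites, checks for severe nausea and vomiting, education of ward nurses on reporting, and entry of adverse events in the data collection tool. On analysis, the Statistics section says: "Intention to treat analysis will be performed".

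**The concern.** The right to leave without giving a reason is ordinary and should stay. This sentence goes further: it tells staff not to ask. It is a stated operating rule, not a detail left to the statistical analysis plan. Two later rules in the same section need the information that it declines to collect.

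Safety is the first thing at stake. The Background Information says that perineural dexamethasone is an off-label use, and that the review it cites on intravenous use found unclear effects on wound healing. Departures caused by harm are therefore worth seeing by arm.

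Interpretation of the primary comparison is the second. Leaving because of pain or nausea is plausibly related to 48-hour opioid use, and leaving for a reason outside the trial is not. Without reasons the two kinds of missing outcome look alike. Keeping the participant's data would not supply the reason.

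**Working it through.** The protocol gives no figure on this point, so there is none to reproduce. The check is whether the stated rules still work for each way of leaving.

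| Way of leaving | Is the reason known? | What happens |
|---|---|---|
| Clinician withdraws the patient because of an adverse event | Yes, from the clinician's own judgement | The follow-up and non-replacement rules can operate |
| Participant leaves; an adverse event is already noticed | Event known, its role in leaving not asked | The event is reported and recorded as such, but the withdrawal is not classed as due to it |
| Participant leaves because of an event not yet recorded | No | Nothing triggers the follow-up rule unless the participant volunteers the reason or the event is found later |
| Participant leaves for an unrelated reason | No | Looks the same as the row above |

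The third row is the gap, and the second gives an incomplete count. Three other statements bear on how well later detection would close it.

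1. The protocol does not say that study examinations, including the six-week one, continue after voluntary withdrawal. It says only that standard post-operative care continues.
2. Under Treatment of subjects, ward nurses are not told which patients are in the trial. Their education on adverse events may therefore not lead them to report an event as a trial event.
3. The data collection tool holds the adverse-event entries. Read literally, the destruction rule covers those entries for a withdrawn participant.

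**Illustration of size.** The only input from the protocol is 60 patients per arm (Trial Design). The rate r of withdrawal due to an adverse event is assumed.

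- Expected number = 60 × r. For r = 1%, 2%, 5%: 0.6, 1.2, 3.
- Chance of at least one = 1 − (1 − r)^60. For the same r: 1 − 0.99^60 = 45.3%; 1 − 0.98^60 = 70.2%; 1 − 0.95^60 = 95.4%.

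These count all withdrawals due to an adverse event. The number missed is only the part not otherwise recorded, and the protocol gives no basis for that fraction.

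As an outer case, suppose that two such withdrawals occurred in the dexamethasone arm and both were missed entirely. The exact (Clopper-Pearson) 95% interval for 0/60 runs from 0 to 1 − 0.025^(1/60) = 5.96%. For 2/60 (3.3%) it runs from 0.41% to 11.53%. The reported upper limit would then be about half what it should be.

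**The case against.** A reader might infer that the protocol forbids recording a reason, contradicts itself, and leaves harm-driven withdrawals impossible to recognise or count by arm. The protocol does not support that reading.

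- The sentence applies to voluntary withdrawal only. The adverse-event rules speak of subjects being withdrawn and follow the clinician route, where the reason is known. Both sets of rules can operate, so there is no strict contradiction.
- Not seeking a reason does not bar staff from recording one that is volunteered or evident.
- Detection of adverse events does not depend on the reason for leaving. All are to be reported, any adverse event leads to unblinding, allocation is held centrally, and injection-site problems and severe nausea are actively looked for. Serious events are followed to resolution without reference to withdrawal.
- The note in the medical record depends on whether the event is thought related to the study drug, not on the participant's stated motive.
- No replacement rule is given for other withdrawals, so a wrong class has no stated consequence for replacement.
- The block is a single injection given to inpatients, so there is no continuing study drug to stop.
- Sensitivity analyses may properly sit in the statistical analysis plan, which is not at hand.

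All of this stands, and it narrows the point. It does not close the third row of the table. If the adverse-event rules cover clinician-initiated withdrawal only, a participant who leaves because of the same harm has no study-physician follow-up under this rule. If they cover voluntary withdrawal too, the protocol gives no means of applying them. A count of adverse events by arm is also not a count of withdrawals due to them.

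The objection is right on one further matter. The destruction rule is the larger obstacle to intention to treat, and a reason written on the data collection form would, read literally, be destroyed with the rest. The remedy has to deal with that.

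**Conclusion.** The concern holds in a limited form. For participant-initiated withdrawal, staff are directed not to seek the reason on which physician-investigator follow-up and non-replacement are conditioned. Events already noticed are captured by other routes. A participant who leaves because of an event not yet recorded may go unrecognised, and withdrawals due to harm are not reliably counted by arm.

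The size cannot be fixed from the protocol. The rates of 1% to 5% are illustrations, and the contrast of 0/60 with 2/60 requires both events to escape the planned surveillance altogether. Neither shows that harms would in fact be lost. This is a minor-to-moderate weakness, worth correcting because the correction is cheap.

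**What to change.** In Selection and withdrawal of subjects, replace the sentence with:

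> Participants need not give a reason for withdrawal; they will be invited, without obligation, to give one. The reason (or refusal), the date and any adverse event present at withdrawal are recorded, and if an adverse event contributed, the adverse-event reporting and follow-up already stated in this section apply.

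In the same section, state that this withdrawal record and any adverse-event record are kept, as consent allows, and are exempt from the rule that data on withdrawn participants are destroyed. Without that exemption the new entry could be lost as soon as it is made. Report reasons for withdrawal by arm.

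The cost is one optional question to a departing participant, one field on the form and matching consent wording. No extra visits, staff or patients are needed, and the right to leave without explanation is kept.

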#### Assessment of safety

Following surgery, adequacy of analgesia will be closely monitored, and inadequate analgesia will be treated as per standard protocol in the postanesthetic care unit (PACU). Physical examination of the TAP block injection sites will be performed daily and at the 6 week postoperative follow up visit. Diabetic patients will have blood glucose monitoring as per standard protocol, and all patients will have serial vital signs four times daily. Clinical assessment for severe postoperative nausea and vomiting (PONV) will be performed as per nursing protocol, and by the attending anesthesiologist on daily round. Any serious adverse events will be followed closely until resolution, with frequency of follow up to be determined by clinical judgement. Education to ward nurses will be provided on identification and reporting of adverse events. Adverse events will be recorded in the data collection tool. All serious adverse events will be reported to the Research Ethics Board and Health Canada as per the University of Saskatchewan Serious Adverse Events Reporting Policy and the Health Canada Guidance for Clinical Trial Sponsors document. Any serious unexpected adverse drug events will be reported to Health Canada. During the course of the trial, the sponsor will inform Health Canada of any serious unexpected adverse drug reaction (SUARD) as follows:

- o (a) if it is neither fatal nor life threatening, within 15 days after becoming aware of the information; and
- o (b) if it is fatal or life threatening, within seven days after becoming aware of the information.

Definitions of reactions are as follows:

Serious Adverse Drug Reaction: An adverse drug reaction that requires in-patient hospitalization or prolongation of existing hospitalization, that causes congenital malformation, that results in persistent or significant disability or incapacity, that is life threatening or that results in death.

Serious Unexpected Adverse Drug Reaction (SUADR): A serious adverse drug reaction that is not identified in nature, severity or frequency in the risk information set out in the investigator's brochure or on the label of the drug.

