#### Data handling and record keeping

All information collected on the data collection form will be de-identified and no direct personal identifiers will be recorded. All measures will be taken to maintain confidentiality on collected data; however, there is a chance of unintentional release of information connecting the subject with the study. A list connecting

the subject's name to the subject study number listed on the data collection form will be stored in a password-protected computed kept in the locked office of the principal investigator, located at Royal University Hospital, Saskatoon. Access to this list will be limited to study staff, and it will be destroyed upon study completion through the confidential paper shredding services of the Royal University Hospital.

Data will be stored for 25 years, as per the Health Canada requirements. The Investigator is responsible to archive the documents/data for the required period of time.

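### Destroying by default the data of participants who withdraw during data collection prevents the stated intention-to-treat analysis, and the rule's reach over adverse events and other kinds of withdrawal is left open

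*Protocol*

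**What the plan says.** All places are in the Protocol.

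- **Selection and withdrawal of subjects**, before allocation: "If this occurs prior to randomization, no patient information will be collected for study purposes".
- Same section, next case: "If withdrawal occurs during data collection, data collected on the subject will be destroyed, and they will continue receiving post-operative care as per standards". No request for erasure is needed and no exception is given. The section also says that participants will not be asked why they leave.
- Same section, further on: the attending surgeon or anesthesiologist may have a patient withdrawn. On adverse events, "All adverse events and protocol deviations will be reported to the study coordinator, study investigators, and appropriate Research Ethics Board". A patient taken out because of such an event is seen by a physician investigator during the hospital stay, and "Subjects withdrawn from the study due to an adverse event will not be replaced".
- **Statistics**, primary outcome: "Intention to treat analysis will be performed".
- **Assessment of safety**: "Adverse events will be recorded in the data collection tool".
- **Data handling and record keeping**: "Data will be stored for 25 years, as per the Health Canada requirements".
- **Trial Design**: 60 patients per arm; PCA use is read at 24 and 48 hours; injection sites are checked at 6 weeks.

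**The concern.** Intention to treat means analysing everyone randomised in the arm to which they were assigned. A rule that deletes a randomised patient's readings removes that patient from any such analysis. The protocol applies it automatically, whether or not the patient wants erasure.

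Three things are at stake. First, the primary comparison shrinks to those who stayed. If leaving is linked to pain, side effects or allocation, the arms are no longer comparable. Because reasons are not sought, there would be little basis for judging whether the loss was informative. Second, the trial's own safety record is exposed: adverse events, unremarkable site checks and the patient's place in the denominator all sit in the trial data. Third, a statistical analysis plan cannot repair this, because it can only choose how to analyse data that the trial still holds.

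**Working it through.** **1. Whom the rule reaches.** The withdrawal text has two cases: before randomisation, when nothing is collected, and during data collection, when what was collected is destroyed. The block is placed before emergence from anesthesia (Treatment of subjects). The outcome data are PACU opioids, PCA and medication-record totals at 24 and 48 hours, and lengths of stay, all of them postoperative (Trial Design). A participant in the second case has therefore been randomised and has received the study block.

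**2. Against the Statistics section.** Intention to treat needs the outcome, or at least the partial outcome, of each randomised patient. Destruction leaves neither. Both statements cannot be carried out for the same patient.

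**3. How long the exposure lasts.** Efficacy follow-up ends at 48 hours, but site assessment runs to 6 weeks. If the 6-week visit counts as data collection, someone who leaves between 48 hours and 6 weeks has a complete primary outcome that the rule would delete.

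**4. Against the safety and storage text.** Adverse events are entered in the data collection tool, so on a plain reading they are data collected on the subject. No exemption is stated. The 25-year storage sentence makes no exception for withdrawn subjects either.

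**5. Possible size (illustration).** The protocol gives no withdrawal rate, so every withdrawal input here is an assumption. Suppose k of 60 controls are deleted and they lie on average 1.5 SD above the full-arm mean. The control mean then falls by 1.5 × k / (60 − k) SD:

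- k = 3: 1.5 × 3 / 57 = 0.079 SD
- k = 6: 1.5 × 6 / 54 = 0.167 SD, and 0.167 / 0.8 = 0.21, about one fifth of the effect size of 0.8 given in the sample-size sentence

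A simulation of 20,000 trials used 60 per arm, a normal outcome, no true difference and a t-test at two-sided 5%, with patients deleted from the control arm only:

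| Deleted from control | Highest users lost: shift (SD) | Type I error | Random loss from upper half: shift (SD) | Type I error |
|---|---|---|---|---|
| 3 (5%) | −0.11 | 9.9% | −0.04 | 5.3% |
| 6 (10%) | −0.19 | 20% | −0.09 | 7.1% |
| 12 (20%) | −0.34 | 49% | −0.20 | 16% |

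The negative sign means that the control arm looks better than it is, so in this example a dexamethasone benefit would be understated. Loss of high users from the dexamethasone arm would reverse the sign.

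**6. Bias, not power.** With a standardised difference of 0.8 and two-sided 5%, power is Φ(0.8 × √(n/2) − 1.96). For n = 60 this is Φ(4.382 − 1.96) = 99.2%. For n = 48 (20% lost per arm) it is Φ(3.919 − 1.96) = 97.5%. More patients would not cure the problem.

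**The case against.** Several stronger readings are tempting, and the protocol does not support them.

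- *The rule applies to every withdrawal.* A reader might infer this from the unqualified wording. But the sentence ends a run of text on participant-initiated withdrawal. Physician and adverse-event withdrawals come afterwards, and the latter have their own provisions on follow-up and non-replacement. Whether the rule covers them is not stated.
- *Safety data are erased.* This goes too far. Adverse events go to the coordinator, the investigators and the ethics board, and serious ones also to Health Canada. Events believed to be drug-related get a note in the medical record. These traces survive outside the trial dataset. What stands is that entries in the data collection tool are not exempted.
- *The readings are lost for good.* Opioid use is taken from the PCA record and the medication administration record, which are hospital records. Nothing says these are destroyed. The barrier to extracting them again would be consent.
- *The 25-year rule is flatly contradicted.* It can be read as the period for whatever is kept. The two sentences need reconciling, but this is not a clear contradiction.

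The bias can also be challenged. Participants are blinded and usual care continues after withdrawal, so leaving because of pain would bring no extra analgesia. If few leave, or they leave at random, little bias arises. This is fair, and it is why the figures above are illustrations and not estimates. It does not remove the conflict with intention to treat. If physician withdrawals are covered, that conflict matters more, because the attending surgeon and anesthesiologist know the allocation.

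**Conclusion.** The concern holds for participants who withdraw during data collection. The default destruction rule prevents the stated intention-to-treat analysis for them, including any whose 48-hour outcome is complete but who leave before the 6-week check. This follows from the text and needs no assumption beyond treating the 6-week visit as data collection for that last group.

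The size and direction of any bias are unknown. Under assumed one-arm losses of 5% to 20%, type I error ranged from 5.3% to 49%, depending on how strongly withdrawal tracks opioid use. The illustration treats the whole 48-hour outcome as lost. For patients who leave before 48 hours, part of that loss would remain under any rule.

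The safety and storage points are narrower. The protocol leaves open whether adverse-event entries and other types of withdrawal fall under the rule, and does not tie the rule to the storage period. The sentence should be corrected before the first withdrawal, because deletion from the trial dataset would then rest on a rule that the protocol itself cannot reconcile with its analysis.

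**What to change.** Replace the destruction sentence with: *If a participant withdraws after randomisation, no further study data are collected without consent; data collected up to withdrawal, including opioid readings and all adverse events, are retained and used in the intention-to-treat and safety analyses, as consent allows.*

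State that this applies to every type of withdrawal: by the participant, by a physician or for an adverse event. Report withdrawals by arm and time. Align the consent form and the storage sentence in Data handling and record keeping with the new text.

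**Cost.** One protocol sentence with its scope statement, and matching consent wording through the ethics board. No extra patients or procedures are needed. Participants lose erasure by default. The consent pages are not available here, so any promise of erasure already made to participants must be checked. The change does not supply a 48-hour total for someone who leaves before 48 hours. Such patients keep only partial readings and still need missing-data handling, which may properly sit in the statistical analysis plan.
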